6.8.3. Electrocardiogram

QT prolongation (defined as QTcF >470) and other ECG abnormalities will be tabulated, displaying the number of subjects with abnormal findings. An abnormal finding is considered to be treatment-emergent if it occurred during treatment and up to 30 days after the last dose.

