Vital signs	Temperature, blood pressure (BP) and heart rate (HR) will be assessed prior to each study treatment dosing 
 On talacotuzumab dosing days BP/HR are measured pre-dose and every 15 min during the first 90 min, and then at 30-min intervals for the remainder of the infusion. For the first infusion, obtain every 30 min post-infusion up to 1.5 hr after the infusion 	X	X	X	

Procedure (Part B)	Notes	Screening Phase	Open-Label Treatment Phase		Follow-up Phase
		Within 28 days before randomization	Day 1 of each cycle (\pm 48 hours) unless otherwise indicated (each cycle = 28 days)	EOT	Every 3 months (\pm 7 days)
Weight	Must be assessed within 3 days prior to dosing on Day 1 of each specified cycle, in case of weight loss of >10% within a cycle, the dose of study drug must be recalculated	X	X	X	
Height		X			
LVEF	MUGA scan is preferred. Echocardiogram can be used if MUGA is not available.	X	as clinically indicated	X	
ECG	QTcF will be assessed at the time of screening. If QTcF is >470 msec, repeat ECG 2 additional times approximately 3 – 5 minutes apart. Average the QTcF of all 3 ECGs to determine if the subject meets the QTc eligibility criteria	X	For subjects in Arm 1, ECG monitoring will occur on Cycle 1 Day 8 and Day 22 after the talacotuzumab IV infusion, then every other cycle thereafter on Day 22 after the talacotuzumab IV infusion. For subjects in Arm 2, ECG monitoring will occur on Cycle 1 Day 5 after the decitabine IV infusion and then every 2 cycles thereafter on Day 5 after the decitabine IV infusion.	X	
Concomitant medications	See Section 8 for detailed instructions; Includes transfusion requirements	Continuous from the time of signing of ICF until 30 days after last study drug dose			Concomitant medications for related AEs of Grade \geq 3 and SAEs regardless of relationship; subsequent anticancer therapy

Procedure (Part B)	Notes	Screening Phase	Open-Label Treatment Phase		Follow-up Phase
		Within 28 days before randomization	Day 1 of each cycle (\pm 48 hours) unless otherwise indicated (each cycle = 28 days)	EOT	Every 3 months (\pm 7 days)
Adverse events	See Section 12 for detailed instructions.	Continuous from the time of signing of ICF until 30 days after last dose of last study drug			Related AEs of Grade \geq 3 and related SAEs; follow until resolution

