4.2. Exclusion Criteria

Any potential subject who meets any of the following criteria will be excluded from participating in the study. These criteria are applicable for both Part A and Part B of the study unless otherwise noted.

1. Acute promyelocytic leukemia with t(15;17), or its molecular equivalent (PML-RAR α).
2. **For Part B only:** Known leukemic involvement or clinical symptoms of leukemic involvement of the central nervous system.

3. Criterion Modified per Amendment 1
 - 3.1 Subjects who received prior treatment with a hypomethylating agent.
4. **For Part A only:** Subjects who did not recover from all clinically significant toxicities (excluding alopecia and hematologic toxicities) of any previous surgery, radiotherapy, targeted therapy, or chemotherapy to less than or equal to Grade 1;
5. Criterion modified per Amendment 1
 - 5.1 Criterion Modified per Amendment 2
 - 5.2 A diagnosis of other malignancy that requires concurrent treatment.
6. Criterion Modified per Amendment 2
 - 6.1. Any uncontrolled active systemic infection that requires treatment with IV antibiotics
7. Criterion Modified per Amendment 1
 - 7.1 A history of human immunodeficiency virus (HIV) antibody positive or tests positive for HIV if tested at screening
8. Criterion Modified per Amendment 2
 - 8.1 Active systemic hepatitis infection requiring treatment or other clinically active liver disease
9. Criterion Modified per Amendment 2
 - 9.1 Criterion modified per Amendment 3
Unstable angina
10. Criterion Removed per Amendment 2
 - 10.1
11. QTcF > 470 ms, or QTcF prolongation at screening deemed clinically relevant by the investigator
12. Criterion modified per Amendment 1
 - 12.1 Criterion Removed per Amendment 2
 - 12.2
13. Known allergies, hypersensitivity, or intolerance to talacotuzumab or decitabine or its excipients^{15,16}
14. Criterion Modified per Amendment 2
 - 14.1 Any condition for which, in the opinion of the investigator, participation would not be in the best interest of the subject (eg, compromise the well-being) or physical limitations that could prevent, limit, or confound the protocol-specified assessments
15. Major surgery, (eg, requiring general anesthesia) within 4 weeks before screening, or will not have fully recovered from surgery, or has surgery planned during the time the subject is expected to participate in the study

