Blood samples for serum chemistry and hematology will be collected as specified in the [Time and Events Schedule Tables 1A and 1B and 1C](#). Additional clinical laboratory tests may be performed as indicated by the overall clinical condition of the subject or if abnormalities warrant more frequent monitoring. Hematology and serum chemistry laboratory evaluations may be repeated as clinically indicated. The investigator must review the laboratory results, document this review, and record any clinically relevant changes occurring during the study in the adverse event section of the eCRF. The laboratory reports must be filed with the source documents. Screening laboratory results must be available to the investigator for evaluation before the first dose of study drug on Day 1 of Cycle 1.

The following tests will be performed by the local laboratory:

- Hematology Panel
 - hemoglobin
 - absolute white blood cell (WBC) count
 - platelet count
 - absolute monocyte count
 - absolute basophil count

- absolute eosinophil count
- absolute neutrophil count
- absolute lymphocyte count
- peripheral blast count
- Coagulation:
 - activated partial thromboplastin time (aPTT)
 - International normalized ratio (INR) or prothrombin time (PT)
- Serum Chemistry Panel

-sodium	-aspartate aminotransferase (AST)
-potassium	-alanine aminotransferase (ALT)
-magnesium	-alkaline phosphatase
-creatinine	-calcium
-total bilirubin	-blood urea nitrogen (BUN)
-phosphate	-uric acid
- Serum β -hCG or urine pregnancy testing for women of childbearing potential only (screening only) or if clinically indicated or required by local regulations.

Electrocardiogram (ECG)

Electrocardiogram will be performed for all subjects during screening as indicated in the [Time and Events Tables 1A](#) and [1B](#). Abnormalities noted at screening should be included in the medical history. During the collection of ECGs, subjects should be in a quiet setting without distractions (eg, television, cell phones). Subjects should rest in a supine position for at least 5 minutes before ECG collection and should refrain from talking or moving arms or legs. If blood sampling or vital sign measurement is scheduled for the same time point as ECG recording, then the procedures should be performed in the following order: ECG(s), vital signs, blood draw.

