5.5. Baseline Value

The last non-missing value collected on or before the day of randomization.

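### SAP 6.8.3 labels ECG abnormalities treatment-emergent by timing alone, so persisting non-QTcF findings from screening count as new; unequal ECG schedules add a modest possible tilt against Arm 1 (minor)

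*SAP*

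**What the plan says.** SAP 6.8.3 plans a count of subjects: "QT prolongation (defined as QTcF >470) and other ECG abnormalities will be tabulated, displaying the number of subjects with abnormal findings". It then defines the label: "An abnormal finding is considered to be treatment-emergent if it occurred during treatment and up to 30 days after the last dose". It does not mention the screening ECG, change from baseline or a shift table.

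A baseline is available. SAP 5.5 defines it as "The last non-missing value collected on or before the day of randomization". The only ECG scheduled before treatment in Part B is at screening, so that ECG is the baseline. Protocol 9.9 says of it: "Abnormalities noted at screening should be included in the medical history". The neighbouring SAP sections do use baseline: 6.8.2 (laboratory) has change from baseline and shifts to worst grade, and 6.8.4 (vital signs) has change from baseline.

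For QTcF there is an entry condition. Protocol 4.2, criterion 11, excludes "QTcF > 470 ms, or QTcF prolongation at screening deemed clinically relevant by the investigator". Table 1B of the Time and Events Schedule adds that a reading above 470 ms is repeated twice: "Average the QTcF of all 3 ECGs to determine if the subject meets the QTc eligibility criteria".

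The on-treatment schedule differs by arm (Table 1B). "For subjects in Arm 1, ECG monitoring will occur on Cycle 1 Day 8 and Day 22 after the talacotuzumab IV infusion", then on Day 22 of every other cycle. "For subjects in Arm 2, ECG monitoring will occur on Cycle 1 Day 5 after the decitabine IV infusion", then on Day 5 every 2 cycles. Both arms also have an ECG at EOT. Protocol 11.11 makes the ECG analysis descriptive only.

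**The concern.** Two features of the planned table need care.

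First, the protocol treats a finding on the screening ECG as medical history, but the SAP would report the same finding as treatment-emergent once it reappears after the first dose. For persisting abnormalities the label would be wrong, and the background they add makes a real difference between arms harder to see.

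Second, a count of subjects with any abnormal ECG depends on how often each subject is recorded. If one arm is recorded more often, or on different days relative to dosing, part of any difference may come from the schedule and not from talacotuzumab.

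The stake is how a two-arm ECG safety table is read. No test, stopping rule or efficacy conclusion depends on it.

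**Working it through.** The documents give no expected ECG abnormality rate, so there is no plan figure to reproduce. All rates below are assumptions, shown as ranges.

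**Step 1: which findings the missing baseline condition reaches.** The SAP cut-off for QT prolongation (QTcF >470) and the exclusion limit (QTcF >470 ms) are the same. An on-treatment QTcF >470 is therefore new, except in a subject with a single screening reading above 470 whose mean of three was not. No entry criterion names any other ECG abnormality. Protocol 4.1 admits subjects aged 65 to 75 with congestive heart failure or ejection fraction ≤50% (one of seven alternative conditions), and Attachment 4 lists atrial fibrillation as an anticipated event. Persisting non-QTcF findings are therefore plausible, but their frequency is unknown.

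**Step 2: dilution.** Let q be the proportion of subjects with a screening abnormality that persists on treatment (equal in both arms in expectation), and t the rate of new abnormalities among the rest. The tabulated rate is q + (1 − q)t. With t = 10% (Arm 1) and 5% (Arm 2), the true ratio is 2.0:

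| q | Arm 1 | Arm 2 | Ratio |
|---|---|---|---|
| 5% | 0.05 + 0.95×0.10 = 14.5% | 0.05 + 0.95×0.05 = 9.75% | 1.49 |
| 10% | 19.0% | 14.5% | 1.31 |
| 20% | 28.0% | 24.0% | 1.17 |
| 30% | 37.0% | 33.5% | 1.10 |

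If t is 10% in both arms, both arms show the same inflated figure (14.5% at q = 5%, 37.0% at q = 30%) and the difference stays at zero.

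**Step 3: number of scheduled ECGs.** I read the later ECGs as falling in Cycles 3, 5, 7 and so on. If n of those cycles are completed, Arm 1 has 2 + n and Arm 2 has 1 + n, plus one each at EOT:

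- 1–2 cycles: 3 vs 2
- 3–4 cycles: 4 vs 3
- 6 cycles: 5 vs 4
- 12 cycles: 8 vs 7

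Within cycles the days (8 and 22 against 5) never coincide. EOT is the one shared on-study time point.

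The extra Arm 1 ECG is not universal. Counting before EOT, a subject who stops between Day 9 and Day 21 of Cycle 1 has one ECG in either arm. One who stops between Day 6 and Day 21 of Cycle 3 has two in either arm. One who stops on Day 6 or 7 of Cycle 1 has none in Arm 1 and one in Arm 2. Arm 1 ECGs are also tied to talacotuzumab infusions, which may be skipped or stopped while decitabine continues.

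**Step 4: effect of one extra ECG with no drug effect.** If ECGs within a subject were independent, with chance p of an abnormal result at each, the chance of at least one in k ECGs is 1 − (1 − p)^k:

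| p | 3 vs 2 ECGs | 4 vs 3 ECGs | 8 vs 7 ECGs |
|---|---|---|---|
| 2% | 5.9% vs 4.0% (1.49) | 7.8% vs 5.9% (1.32) | 14.9% vs 13.2% (1.13) |
| 5% | 14.3% vs 9.8% (1.46) | 18.5% vs 14.3% (1.30) | 33.7% vs 30.2% (1.12) |
| 10% | 27.1% vs 19.0% (1.43) | 34.4% vs 27.1% (1.27) | 57.0% vs 52.2% (1.09) |

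At the other extreme, if a subject's result is the same on every ECG, each arm shows p and the ratio is 1.0. The truth lies between, and the documents do not say where.

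**The case against.** The strongest reply is that little depends on this table. ECG data are descriptive, and ECG change is not among the adverse events of special interest in SAP 5.16. Protocol 9.9 requires clinically relevant changes to be recorded as adverse events, and Protocol 11.11 summarises events with onset on treatment or worsening since baseline. That route would capture most new and important ECG changes. This stands, and it sets the severity.

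A second reply is that a finding which occurred during treatment can be read as one with onset during treatment, in parallel with the adverse-event definition in SAP 5.15. That reading is possible, but the text does not state it. A programmer following the sentence literally would flag every abnormal on-treatment tracing.

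A reader might also infer stronger claims that the documents do not support:

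- *The whole table is inflated.* QTcF >470, the only abnormality that 6.8.3 names, is screened out at the same cut-off.
- *The arms share no ECG time point.* Both have an EOT ECG, normally within the 30-day window, although a visit on days 31 to 37 would fall outside it.
- *Arm 1 always has one more ECG.* Step 3 shows subjects for whom this fails.
- *Pre-existing findings bias the comparison or swamp it.* Randomization balances them in expectation, and at 5% prevalence the tabulated ratio is still 1.49.

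**Conclusion.** The concern holds in a limited form. Read literally, SAP 6.8.3 would label persisting non-QTcF abnormalities as treatment-emergent. This dilutes a between-arm difference without creating one: a true ratio of 2.0 is tabulated as 1.49 to 1.10 for an assumed prevalence of 5% to 30% and assumed new rates of 10% vs 5%.

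The unequal schedule can tilt the any-abnormality count modestly against Arm 1, and this applies to QTcF as well. At 4 cycles plus EOT, the ratio with no drug effect runs from 1.0 under full persistence to about 1.3 under independence. Under independence it is nearer 1.5 at 1–2 cycles and 1.1 at 12 cycles.

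Both ranges rest on rates that the documents do not give. It would go too far to say that the table cannot show whether talacotuzumab affects the ECG. Severity is minor, confined to descriptive safety reporting.

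**What to change.** In SAP 6.8.3, define a treatment-emergent ECG abnormality as one absent, or less severe, on the baseline ECG (SAP 5.5) and present after the first dose and no later than 30 days after the last. Alternatively, add a baseline-to-worst shift table, as 6.8.2 already does for laboratory data. Where three screening ECGs were taken, state which QTcF value serves as baseline.

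Keep every ECG in the report. Present results by scheduled visit within each arm, with the cycle day labelled and the number of subjects assessed, and show EOT as the common time point. Removing Arm 1 Cycle 1 Day 8 from the between-arm count would equalise the number of ECGs, but it would take out the ECG after the first talacotuzumab infusion and still compare Day 22 with Day 5. It is not recommended.

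The cost is SAP wording and table programming, with no new data collection. One limit remains: Table 1C lists no ECG during Amendment 6, so subjects still on treatment then may lack an EOT ECG. The number assessed at EOT will show this.

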6.8.4. Vital Signs

Descriptive statistics of weight, heart rate, temperature and supine blood pressure (systolic and diastolic) values and changes from baseline will be descriptively summarized by treatment arm at each time point.

